## SUMMARY OF CHANGES

The following changes have been made to this protocol since the first approved protocol version. Changes in more detail can be seen in separate Summary of Changes document(s).

Previous Protocol version and date	Revised Protocol version and date	Description of Change(s)
v1.0, 17Dec2020	v2.0, 05Feb2021	
Substantial changes
 
Study treatment in accordance with standard treatment guidelines updated according to FDA recommendations and concomitant baricitinib usage with study IMP prohibited. Systemic baricitinib therapy have been added to the exclusion criteria and exclusion criteria have been further updated to better equate the clinical routine care. MxA, CD73, PIMs (D3), Interferon beta and SARS-CoV-2 sample collection timepoints and the list of PIMs have been updated. Analyses of PIMs and interferon signalling markers using the Nanostring technology has been added.
 
Non-substantial changes
 
Text about oxygen support and mechanical ventilation on Day 28 has been added to the exploratory outcome measures where incoherently described. Age stratification classes specified in the randomization criteria. Table 2 has been updated to be more readable and regarding the chapters 6.2 – 6.5 the chapter order has been rearranged, and text clarified. Also other non-substantial text clarifications and correction of typos have been made through the protocol.

v2.0, 05Feb2021	v3.0, 14Jun2021	
The comparator group is changed to dexamethasone and the protocol is updated throughout to match this change. Eligibility criteria updated to exclude patients not requiring supplemental oxygen. Incidence of study treatment discontinuation and transition to an open label corticosteroid is added as exploratory efficacy endpoint. X-ray/CT scans performed as part of standard clinical care are used for COVID-19 diagnostics accuracy, separate X-ray/CT scans are not performed for study purpose. A positive test for COVID-19 must be available for randomization, but now specified that it can be other than a PCR test. Nasal swab sampling and local analysis for viral load is exchanged to serum sampling and analysis at a central laboratory (the maximum additional blood sampling equals 12.5 ml). The AE follow-up period and pregnancy reporting period are further specified.

		
Statistical analyses section has been updated with the description of analysing also the use of unblinded corticosteroids as an intercurrent event. Global Co-ordinating investigators is updated with [name], University of Colorado.
 
Also other non-substantial text clarifications and correction of typos have been made throughout the protocol.

v3.0, 14Jun2021	v4.0, 27Sep2021	
A baseline nasopharyngeal swab is added for analysis of SARS-CoV-2 variants. All-cause mortality at Days 28 and 90 are added to the secondary endpoints, and efficacy of study treatment based on viral variant and on vaccination status to the exploratory endpoints. The text in inclusion criteria 4 is harmonized with inclusion criteria 3 for better clarity by both referring to respiratory symptoms. Blood sampling for SARS-CoV-2 viral burden is changed from Day 4 to Day 3 to harmonize with other blood sampling. Assessments on subjects that are discharged from the hospital but re-admitted due to COVID-19 have been specified. Description of the study design and risk-benefit assessment are adapted according to FDA's recommendations. Specified that in addition to baricitinib, also concomitant tofacitinib (and other JAK-STAT signalling pathway inhibitors) usage with study IMP is prohibited. Updated that patients who have received at least one dose of study drug will not be replaced for any reasons.
 
Also, other text clarifications and correction of typos have been made through the protocol.

## LIST OF ABBREVIATIONS AND DEFINITIONS OF TERMS

ADA	Anti-Drug Antibodies
AE	Adverse Event
AEP	Acute Eosinophilic Pneumonia
AKI	Acute Kidney Injury
ALI	Acute Lung Injury
ARDS	Acute Respiratory Distress Syndrome
BIPAP	Bilevel Positive Airway Pressure
BP	Blood Pressure
CBC	Complete Blood Count
CD73	Cluster of differentiation 73
CI	Confidence Interval
CPAP	Continuous Positive Airway Pressure
CRA	Clinical Research Associate (Monitor)
CT	Computerised Tomography
D	Day (as in treatment day)
DNR	Do Not Resuscitate
ECG	Electrocardiogram
ECOG	Eastern Cooperative Oncology Group
ECMO	Extracorporeal membrane oxygenation
e-CRF	Electronic Case Report Form
FAS	Full Analysis Set
FU	Follow-up
HR	Heart Rate
HSP	Hypersensitivity Pneumonitis
ICD	Informed Consent Document
ICH	International Conference on Harmonisation
ICU	Intensive Care Unit
IDMC	Independent Data Monitoring Committee
IEC	Independent Ethics Committee
IFN	Interferon
IRB	Institutional Review Board
IMP	Investigational Medicinal Product

---

IV	Intravenous
IWRS	Interactive Web-Response System
JAK-STAT	Janus kinase-signal transducer and activator of transcription
MERS	Middle East Respiratory Syndrome
MIU	Million International Units
MOF	Multiple Organ Failure
MM	Medical Monitor
MxA	Myxovirus resistance protein A
NOAEL	No Observed Adverse-Effect Level
OSCI	WHO ordinal scale for clinical improvement
OTD	Optimum Tolerated Dose
PBMC	Peripheral Blood Mononuclear Cells
PCR	Polymerase Chain Reaction
PerLR	Personal Legal Representative
PD	Pharmacodynamics
PIM	Potential Inflammatory Marker
PPS	Per-Protocol Set
PrfLR	Professional Legal Representative
RRT	Renal Replacement Therapy
SAE	Serious Adverse Event
SAP	Statistical Analysis Plan
SD	Standard Deviation
SUSAR	Suspected Unexpected Serious Adverse Reaction
TEAE	Treatment-Emergent Adverse Event
WBC	White Blood Cells

## 1 PROTOCOL SYNOPSIS

Title	A Phase II Multi-Center, Double-Blind, Randomized and Controlled Study of the Safety and Efficacy of Intravenous Recombinant Human Interferon Beta-1a in Comparison to Dexamethasone for the Treatment of Hospitalized Patients with COVID-19 Infection
Sponsor Study No.	FP1CLI017
Phase	II
Funding/Support	U.S. Department of Defense and Faron Pharmaceuticals Ltd.
Sponsor	Faron Pharmaceuticals Ltd., Turku, Finland
Co-ordinating Investigators	[name], Harvard Medical School [name], University of Colorado School of Medicine
Study Centre(s)	Approximately 5-15 investigational sites located in the USA and possibly also in other countries
Objectives	
Primary Objectives	

- To demonstrate the safety and tolerability of early intravenous (IV) IFN beta-1a administration in hospitalized patients with COVID-19 infection compared to dexamethasone

- To investigate the efficacy of IV IFN beta-1a to improve clinical status in hospitalized patients with COVID-19 compared to dexamethasone

Secondary Objectives	

- To assess the immunogenicity of IFN beta-1a

- To investigate the efficacy of IV IFN beta-1a on clinical outcomes in hospitalized patients with COVID-19 compared to dexamethasone

Exploratory Objectives	

- To investigate the efficacy of IV IFN beta-1a on additional clinical outcomes in hospitalized patients with COVID-19 compared to dexamethasone

- To investigate study treatment discontinuation rate of IFN beta-1a compared to dexamethasone

- To investigate the effect of IMPs on viral burden (quantitative) in blood during the disease course

- To measure the pharmacodynamic (PD) effects of IFN beta-1a (Myxovirus Resistance Protein A (MxA) and cluster of differentiation 73 (CD73)

- To measure IFN beta levels during the treatment

- To evaluate potential inflammatory markers (PIMs) and interferon signalling markers at protein and RNA level in response to treatment

- To evaluate genetic susceptibility to IFN beta-1a treatment
- To investigate the efficacy of study treatment based on SARS-CoV-2 variant
- To investigate the efficacy of study treatment based on the vaccination status

**Design**

This is a multi-center, double-blind, randomized and controlled trial of early IV administration of IFN beta-1a compared with dexamethasone in hospitalized patients with COVID-19 infection not requiring high-flow (> 8L/min) oxygen therapy or mechanical ventilation.

COVID-19 patients in the Emergency Department (ED) or early in hospitalization will undergo screening during which informed consent will be obtained and eligibility assessed by Inclusion and Exclusion criteria. No more than 48 hours may elapse between hospital arrival of the patient and administration of the first dose of the study drug.

At randomization, subjects will be stratified by gender and age to be treated daily either with IV IFN beta-1a 10 µg or IV dexamethasone 6 mg for 6 days while hospitalized and will undergo daily assessments while in hospital for a maximum of 28 days. Study specific assessments will be collected at pre-dose Day 1 through Day 28, in addition, clinical routine assessments will be utilized for safety and efficacy assessments.

Due to preclinical and clinical data demonstrating that concomitant administration of systemic corticosteroids diminishes the effectiveness of IV IFN beta-1a, systemic open-label corticosteroids are not permitted during the 6-day acute intervention period. The requirement for systemic open-label corticosteroid treatment is an exclusion criterion in the study. However, if the Investigator/attending clinician determines that the subject requires open-label corticosteroids during the intervention period (Study Day 1 - Day 6), the investigational medicinal products (IMPs) will be discontinued, and the subject will continue to have the ongoing study assessments. From Day 7 onward corticosteroid treatment will be permitted if required according to the judgment of the treating attending clinician. Same principle should be applied for other co-medications with potential of interacting with IFN beta-1a, such as baricitinib, tofacitinib and other inhibitors of *janus kinase*-signal transducer and activator of transcription (JAK-STAT) signalling pathway.

Specific medical conditions that require immediate corticosteroid treatment are specified in the protocol. Once diagnosed, treatment with IMP should be discontinued and the subjects will continue to have the ongoing study assessments.

Standard treatment practice of COVID-19 should follow treatment guidelines, and should a study patient progress in disease severity requiring increasing amounts of supplemental oxygen, the study medication should be stopped and dexamethasone treatment should

begin according to guidelines (<https://www.covid19treatmentguidelines.nih.gov/therapeutic-management>). Remdesivir does not impact study treatment.

The main analysis and reporting will use Day 28 data after the last study subject has completed the Day 28 assessments.

An Independent Data Monitoring Committee (IDMC) will be established to monitor safety on an ongoing basis.

## Study treatments

Investigational medicinal products (IMPs):

- IFN beta-1a 10 µg (recombinant human IFN beta-1a) or Dexamethasone 6 mg will be administered once daily as an IV bolus injection for 6 days.
- To maintain blinding at administration, every study subject will receive two separate bolus injections of IMP (either IFN-beta - 1a/saline, and another injection of Saline/Dexamethasone). Study IMPs will be prepared by an unblinded person according to the randomization code.

## Number of Study subjects

140 subjects with COVID-19 infection will be randomized at approximately 5-15 investigational sites.

## Population

The inclusion and exclusion criteria apply during screening and prior to administration of the first dose of study drug on Day 1.

## Inclusion Criteria

1. Age  $\geq$ 18 years
2. Positive SARS-CoV-2 test by PCR (polymerase chain reaction) or other diagnostic method within the past 7 days
3. Admission to hospital with respiratory symptoms of COVID-19 requiring hospital care and oxygen supplementation ( $\leq$  8L/min)
4. Respiratory symptom onset no more than 7 days prior to hospital arrival
5. Informed consent from the subject or the subject's personal legal representative or a professional legal representative must be available

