## 2.4 Dexamethasone

### 2.4.1 Clinical safety experience of Dexamethasone

I.V dexamethasone is recommended therapy for hospitalized patients with hypoxemia who are receiving oxygen through a high-flow device, or non-invasive ventilation, or invasive ventilation. It is also recommended for patients receiving increasing amounts of supplemental oxygen therapy (<https://www.covid19treatmentguidelines.nih.gov/therapies/immunomodulators/corticosteroids/>). It has been proposed that the potent anti-inflammatory effects of corticosteroids might prevent or mitigate the deleterious systemic inflammatory effects in patients with severe form of COVID-19.

The incidence of side effects associated with the use of dexamethasone generally correlates with dosage, timing of administration, and duration of treatment. The most commonly occurring side effects of dexamethasone have included a wide range of psychiatric reactions, psychotic reactions, behavioural disturbances, irritability, anxiety, sleep disturbances and cognitive dysfunction including confusion and amnesia, decreased blood eosinophils and lymphocytes, increased infection susceptibility, masking of infection signs, aggravated infection, and fungal infections of mucous membranes and the skin. In adults the frequency of severe reactions has been estimated to be 5-6%.

In this study, 6 mg IV doses of dexamethasone will be administered for 6 days. Adverse reactions associated with the use of glucocorticoids are usually dependent on the dose and the duration of the

treatment. Treatment duration of 6 days is relatively short, and the occurrence of the above-mentioned reactions associated with long-term use is unlikely.

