## 4 OVERALL DESIGN AND PLAN OF THE STUDY

### 4.1 Overview

This is a multicentre Phase II, double-blind, randomized and controlled, study of the safety and preliminary efficacy of IV IFN beta-1a compared with dexamethasone in adult patients diagnosed with COVID-19 needing hospitalization, but not invasive mechanical ventilation or high flow/presurized supplemental oxygen. The primary endpoint safety and tolerability of IV IFN beta-

1a, and primary efficacy endpoint is WHO ordinal scale for clinical improvement (WHO OSCI) score at D14. Both treatment groups will receive standard care according to current treatment guidelines, except open-label corticosteroids during study days D1-D6 (or other co-medication with potential of interacting with IFN beta-1a; [Section 5.7](#)). If the patient receives (oral or intravenous) glucocorticoids during study days D1-D6, the IMP will be discontinued, and the patient will continue with in all follow-up study assessments.

[figure not shown]
Approximately 140 subjects are planned. Patients with COVID-19 admitted to hospital will undergo screening during which written informed consent will be obtained and eligibility assessed. Not more than 48 hours may elapse between arrival to hospital and administration of the first dose of study drug. An interactive web-response system (IWRS) will be used to randomise the patients using age and gender as stratification parameters.

Following randomization, patients will be treated daily with IFN beta-1a 10 µg or dexamethasone 6 mg as an IV bolus for 6 days and will undergo daily assessments while hospitalized. The main analysis and reporting will use D14 and D28 data. D90 data will be analysed separately. Final follow-up will occur at D90 by phone or through medical records. The overall duration of the study for a patient is therefore 3 months. During the long-term follow-up periods patient care will follow normal hospital procedures, as appropriate. The study will be completed when the last patient completes D90 study assessment. The study design is summarised in [Figure 1](#).

Discontinuation criteria for individual patients and the entire study are described in [Section 4.8.1](#).

The study design incorporates an Independent Data Monitoring Committee (IDMC) that will review ongoing safety (i.e., adverse events [AEs] and serious AEs [SAEs]) and will also make recommendations to the Sponsor as described in the IDMC charter. Details of the IDMC are given in [Section 8.8](#).

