### 4.3 Justification of the Study Design

This is a Phase II study to evaluate the safety and efficacy of IFN beta-1a in comparison to dexamethasone in the treatment of subjects with COVID-19. The study is designed as a double-blind, randomized, parallel-group, controlled, multicentre clinical study.

At present there is no approved pharmacological treatment for the prevention of ARDS. The only currently available treatment for mechanically ventilated COVID-19 patients is dexamethasone, but still COVID-19 mortality to ARDS remains high. Because of the lack of an effective pharmacological agent, glucocorticoids are widely used because of their anti-inflammatory properties. However, they may dampen natural anti-viral response of IFN beta signalling. Further, overlapping use of glucocorticoids may block IFN beta-1a from up-regulating CD73 on the lung endothelium. Therefore, the current approach is to investigate the use of IFN beta-1a before corticosteroids (or other medications with immunosuppressive activity) are indicated for COVID-19 and to prevent disease aggravation to ARDS.

The study target population is defined to subjects requiring oxygen supplementation (< 8 l/min) in order to comply with the treatment guidelines (<https://www.covid19treatmentguidelines.nih.gov/therapeutic-management/>). The IFN beta-1a treatment arm is not to receive dexamethasone for study days D1-D6. This is justified with the anticipated anti-viral effects of IFN beta and clinical observations of severity of the disease associated with a deficiency in IFN signalling, and uncertainty of the benefit from dexamethasone in mild COVID-19 (see [Section 2.6](#) for detailed justification for the study setting). However, should the study subjects condition worsen during the early course of the study, while the IMP is being administered (Study days D1-D6), the IMP can be discontinued and dexamethasone initiated according to the discretion of the attending physician, ideally after a discussion with the local study investigator, if the clinical condition of the patient permits it.

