#### 4.6 Exclusion Criteria

1. Unable to screen, randomize and administer study drug within 48 hours from arrival to hospital
2. Systemic corticosteroid, baricitinib or tofacitinib (or other JAK-STAT signalling pathway inhibitors) therapy within 7 days prior to arrival to hospital or planned for the next days
3. Known hypersensitivity or contraindication to natural or recombinant IFN-beta-1a or its excipients, or to dexamethasone or its excipients
4. Currently receiving IFN-beta-1a therapy
5. Home assisted ventilation (via tracheotomy or non-invasive) except for Continuous positive airway pressure (CPAP) / Bilevel Positive Airway Pressure (BIPAP) used only for sleep-disordered breathing
6. Participation in another concurrent interventional pharmacotherapy trial during the study period
7. Decision to withhold life-sustaining treatment; patient not committed to full support (except DNR after cardiac arrest only)
8. Woman known to be pregnant, lactating or with a positive pregnancy test (urine or serum test)
9. Subject is not expected to survive for 24 hours
10. Subject has liver failure (Child–Pugh grade C)
11. Any clinical condition that in the opinion of the attending clinician or Investigator would present a risk for the patient to participate in the study

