#### 4.7 Confirmation of Patient Eligibility

To ensure appropriate enrolment into the study there will be a formal confirmation of eligibility process utilising the following procedure:

An electronic Case Report Form (e-CRF) with mandatory fields for completion and a checklist of inclusion and exclusion criteria; all items will need to be completed. The IWRS System will prompt the Investigator to confirm eligibility before allowing a patient to progress to randomization.

With this method, only those patients whose data are recorded as meeting eligibility criteria can be randomized.

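### The population statement excludes high-flow and pressurised oxygen, but the listed criteria limit only oxygen flow and exclude only home ventilation, so a patient on in-hospital CPAP/BIPAP can qualify

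*Protocol*

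**What the plan says.** **Population statements.** Section 4.1 describes adults with COVID-19 "needing hospitalization, but not invasive mechanical ventilation or high flow/presurized supplemental oxygen". SAP section 4 carries the same restriction. The synopsis Design paragraph is narrower: "not requiring high-flow (> 8L/min) oxygen therapy or mechanical ventilation". It does not mention pressurised oxygen or say whether mechanical ventilation includes non-invasive ventilation.

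**Listed criteria.** Inclusion 3 is the same in the synopsis and Section 4.5: "Admission to hospital with respiratory symptoms of COVID-19 requiring hospital care and oxygen supplementation", followed by a limit of 8 L/min or less. The only exclusion that names ventilation is number 5, which begins "Home assisted ventilation (via tracheotomy or non-invasive) except for Continuous positive airway pressure (CPAP" and goes on to except CPAP/BIPAP used solely for sleep-disordered breathing.

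**What decides entry.** Section 4.4 requires all inclusion criteria and no exclusion criterion. Section 4.7 puts a checklist of those criteria in the e-CRF, has the IWRS ask the investigator to confirm eligibility, and concludes that "only those patients whose data are recorded as meeting eligibility criteria can be randomized". Section 6.2.2 repeats the criteria check before the first dose.

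**Related text.** Section 4.3 describes the target population as "subjects requiring oxygen supplementation (< 8 l/min". Section 4.8.2 gives deterioration to mechanical ventilation before the first dose as an example of a randomised subject becoming ineligible. Section 2.4.1 reports dexamethasone as recommended for patients "receiving oxygen through a high-flow device, or non-invasive ventilation, or invasive ventilation". Section 2.6 includes non-invasive ventilation among the signs of deterioration at which interferon patients will receive dexamethasone.

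**The concern.** A site enrols from the criteria, not from the design overview. If the overview contains a restriction that the criteria lack, a site that follows the checklist exactly can enrol a patient whom the design says is not in the trial, and no deviation would be recorded.

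Two things are at stake. First, the risk/benefit argument in Section 2.6 is made for patients on low levels of oxygen. It accepts withholding dexamethasone from the interferon arm because the benefit at that level is uncertain, and promises dexamethasone on deterioration. A patient who enters on non-invasive ventilation is already in a state that Section 2.6 lists as deterioration, so the argument does not cover that patient.

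Second, the gap reaches the analysis set. Section 7.1.3 removes from the full analysis set, and replaces, a randomised subject who becomes ineligible before dosing. If loss of eligibility depends on a ventilation rule that is not among the criteria, sites may apply it differently, for example to a patient who starts CPAP between randomisation and dosing.

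**Working it through.** No arithmetic applies. The check sets the passages side by side and then takes one patient through the criteria.

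**Step 1. Which types of support does each text address?**

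| Support at entry | Section 4.1 and SAP section 4 | Synopsis Design | Inclusion and exclusion criteria |
|---|---|---|---|
| Oxygen flow above 8 L/min | out, as high flow (no figure given) | out | out (inclusion 3) |
| Pressurised oxygen, started in hospital | out | not clear | not named |
| Invasive ventilation, started in hospital | out | out | not named |
| Home ventilation | not addressed separately | not addressed separately | out (exclusion 5), except for sleep-disordered breathing |

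The middle two rows are the gap. For pressurised support the point rests on Section 4.1 and the SAP, because the synopsis is ambiguous.

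**Step 2. One patient against the list.** Take an adult with a recent positive test, respiratory symptoms within the allowed period and consent given, started on CPAP after arrival with oxygen supplied below 8 L/min. Choosing a flow below 8 keeps the difference between Sections 4.3 and 4.5 out of the question.

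- Inclusions 1, 2, 4 and 5: met by construction.
- Inclusion 3: the patient needs hospital care and oxygen, and the flow is within the limit. Met as worded.
- Exclusion 5: does not apply, because the support began in hospital.
- Exclusions 1, 3, 4 and 6 to 10 (timing, hypersensitivity, current interferon, another trial, limits on life support, pregnancy, survival under 24 hours, liver failure): none turns on the mode of respiratory support.
- Exclusion 2: applies if a systemic corticosteroid or JAK inhibitor was given in the preceding 7 days or is planned.
- Exclusion 11: applies if the clinician or investigator sees a risk.

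Only exclusions 2 and 11 can stop this patient on account of the ventilatory support. Exclusion 2 depends on what the clinician plans and exclusion 11 on judgement. If neither is invoked, the patient meets every listed criterion and is outside the Section 4.1 population.

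**Step 3. Does another passage close the gap?** Section 4.8.2 defines a screen failure as failure to comply with the criteria, then gives mechanical ventilation as its example. That shows the intention, but the criteria do not contain it. The WHO scale separates level 4 (supplemental oxygen) from level 5 (non-invasive ventilation or high-flow devices) and is scored before dosing (Table 2, Section 6.2.2), yet no criterion refers to the score.

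**Step 4. The flow limit.** Section 4.3 says below 8 L/min; the synopsis and Section 4.5 say 8 or less. A patient at exactly 8 L/min is outside the first and inside the second. No other flow is affected.

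**The case against.** The strongest reply is that the protocol already keeps most of these patients out. Section 5.7 calls for care in line with the treatment guidelines, and Section 2.4.1 reports dexamethasone as recommended on non-invasive ventilation. A clinician who follows both will usually have a corticosteroid planned, and exclusion 2 then applies. Exclusion 11 is a further safeguard. In addition, the WHO scale makes supplemental oxygen a separate level from non-invasive ventilation, so inclusion 3 can naturally be read as meaning level 4 only.

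Much of this stands. It narrows the gap but does not close it: exclusion 2 depends on intent, and a clinician willing to enrol into a trial with blinded dexamethasone in one arm need not plan it open-label; exclusion 11 is discretionary; and inclusion 3 does not refer to the scale.

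A reader might infer more than the documents support:

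- *That patients on pressurised support meet the criteria as a rule.* They can, under the conditions in Step 2. Many would be stopped by exclusion 2.
- *That a patient ventilated by oxygen fraction, with no L/min value, also qualifies.* Inclusion criteria must be positively met, and such a patient has not been shown to satisfy a limit stated in L/min.
- *That power falls by a calculable amount.* No entry rate is given. A dilution figure would also have to assume that study drug stops at once and has no effect in every affected patient, which the documents do not establish.
- *That the enrolled set would cease to be a low-flow population.* A few possible entrants do not show that. They would be visible in the pre-dose WHO score, which is a covariate in the primary model (Section 7.5.1).

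**Conclusion.** The point holds as a mismatch between the population statement and the criteria that carry it out. Followed literally, the checklist can admit a patient whom Section 4.1 and the SAP place outside the trial and whom the Section 2.6 argument does not cover. Section 4.8.2 relies on a ventilation criterion that is not listed, and the flow limit conflicts at exactly 8 L/min.

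The documents do not allow the effect to be sized. The number of affected patients is probably small given exclusions 2 and 11, so this is a point about eligibility and consistency, not about power. It also concerns the plan as written: SAP section 2 records termination with five patients dosed, and SAP section 6 provides for descriptive presentation only, so no consequence for the reported results is claimed.

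The conclusion assumes that the listed criteria are decisive, as Sections 4.4 and 4.7 say, and that inclusion 3 means no more than its words. It takes no view on which respiratory-support limit or flow value is clinically right.

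**What to change.** Reconcile the criteria in the synopsis and Sections 4.5 and 4.6 with the population statement in Section 4.1, so that the restriction on ventilatory support is an explicit criterion. Keep the exception for sleep-disordered breathing that exclusion 5 already contains. Say in the synopsis Design paragraph whether mechanical ventilation includes non-invasive ventilation.

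Add the matching item to the e-CRF eligibility checklist of Section 4.7, confirmed through the IWRS and rechecked before dosing under Section 6.2.2. Refer Section 4.8.2 to that criterion, so that loss of eligibility after randomisation, and with it removal from the full analysis set, rests on a listed rule.

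Reconcile the flow limit in Section 4.3 with the synopsis and Section 4.5. The choice of limit is for the sponsor.

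The cost is one clause in an amendment, one checklist item and a few wording corrections. No new data are needed, because the WHO score and clinical status are already recorded before the first dose. No patient whom the Section 4.1 design intends to enrol is lost, because its text already leaves these patients out.
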